5.2.8 Exposures, outcomes and covariates

1) Advice & Guidance

Please see 4.2.8

2) Direct referral

Please see 4.2.8

NIHR 158681BADGER			
Protocol Version 2.0 18/06/2024	CPMS: 58336	IRAS No: 333799	CPRD ID: 24_004022

3) Tracer conditions

Relevant codes for tracer conditions will be derived from existing code lists (e.g. those already held at Keele and / or using open access lists such as those held by OpenCodelists) or developed and validated through consensus of EHR researchers and clinical academics within the study team and the EHR Research Group at Keele University, a group led by co-applicants KJ and KM. This research group has set procedures for developing code lists. Codes for covariates and outcomes will be derived in a similar process.

5.3 DATA / STATISTICAL ANALYSIS

For WP2a, the outcome for those with an A&G and/or direct referral recorded will be the time to diagnosis from the first recorded A&G or direct referral to index diagnosis date. We will calculate median (interquartile range) days to diagnosis from first recorded A&G or direct referral code and incidence rates per 1,000 person years and present with 95% confidence intervals. We will use flexible parametric survival analysis to compare A&G and direct referral on time to diagnosis. Flexible parametric survival analyses are preferred to Cox proportional hazards regression as they allow easier modelling of time-dependent effects and the ability to determine absolute risks of outcome. Exposure' will be the initial method of referral (A&G, direct referral) prior to index date. Hazard ratios will be presented as unadjusted and adjusted for covariates with 95% confidence intervals (CI).

For WP 2b, individuals with each index condition will be categorised as i) A&G only, ii) direct referral only, iii) A&G and direct referral, iv) no recorded A&G or direct referral in the 24 months before diagnosis:

- negative binomial or zero-inflated negative binomial regression will be used to estimate incidence rate ratios for the number of consultations, referrals and prescriptions in primary care, and number of outpatient appointments,
- robust Poisson regression will be used to compare A&E and unplanned admission in secondary care;
- flexible parametric survival analysis will estimate hazard ratios for mortality.

Rates or ratios will be presented as unadjusted and adjusted for covariates with 95% CI.

As part of the Study Within A Project (SWAP) (see Section 8), the impact of multimorbidity and frailty on decision to use A&G and its outcomes will be considered by including multimorbidity and frailty (defined by Charlson comorbidity index/number of prescriptions and electronic frailty index) as predictors and moderators of A&G outcome in the models.

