4.2.5 Sample size considerations

The feasibility count of 975,000 individuals gives an estimated mean of 108,000 per annum over the nine years of the study. Assuming an annual denominator population of 14 million (and hence prevalence of A&G of approximately 800/100,000), then per annum 95% confidence limits for the prevalence of A&G will be \pm 5/100,000. For assessing percentage of A&Gs which result in a referral, assuming an estimate of 50%, then per annum 95% confidence limits will be \pm 0.3% overall and \pm 3% for a lowest covariate (e.g., ethnicity group) category prevalence of 1%.

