4.2.8 Exposures, outcomes and covariates

1) Advice & Guidance

We will determine coded A&G events and, where possible, the specialty linked to the A&G. When a Choose and Book referral is made through e-RS (by selecting either the satellite button for "advice and guidance" which equates to an A&G request or the "Refer/Advice" satellite button which equates to the standard or direct referral to secondary care), the referral must be saved before the activity can be completed and exited back to the clinical software system. To save the activity, a code must be entered to then move back into another part of the healthcare record. For A&G requests, the coded term is "Advice and guidance requested." We will also include in our codelist the code "Advice and guidance received" which we will use to indicate A&G if the patient does not have an "Advice and guidance requested" code within the same study time period. We will map A&G to specialty (e.g. rheumatology, neurology) and type of health condition (e.g. musculoskeletal, cardiovascular). Given A&G coded events may not routinely have the specialty recorded we will use information from direct referrals (sampled from 3 specified years - 2015, 2019, 2023 - within our study period) as the basis for mapping to specialty. We will first determine morbidity/symptom codes recorded on the date of all direct referrals (defined below) with a named specialty, or in the prior 2 weeks. We will determine which Read or SNOMED CT codes are most frequently recorded with referral to each specialty and use these to map (impute) specialties in those with an A&G event based on matching these codes to Read/SNOMED CT morbidity or symptom codes recorded on the date of A&G or in the prior 2 weeks. Where the specialty is still unknown after this mapping exercise, we will review all codes in the 2 weeks prior to or on date of A&G request and agree on specialty (guided by Read code chapter) by consensus or define as unknown if no consensus. Type of health condition will be based on specialty or morbidity/symptom code at date of A&G event.

2) Direct referral

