To derive the comparative prevalence and incidence of elective referrals, direct routine referrals will be determined using codes with a term indicating a referral and defined by consensus of study team to indicate a routine referral to a specialty (i.e. not fast track or referral with an intention to admit / emergency referral). To ascertain A&G events which result in a direct referral, we will determine

NIHR 158681BADGER			
Protocol Version 2.0 18/06/2024	CPMS: 58336	IRAS No: 333799	CPRD ID: 24_004022

referrals within 122 days (4 months) after date of an A&G request. These will be defined as i) a direct referral code defined as above and by ii) linking events in the Referrals table to the Observation table and determining duration of time between the linked observation event and the A&G request date. We will also determine referrals within 122 days (4 months) before an A&G request to see how often A&G requests follow a referral request. As a sensitivity analysis we will repeat for 365 days (12 months) either side of the A&G request date. Code lists for A&G have been derived and used in our CPRD feasibility study (FS_002830). The draft code list for direct referral has also been developed. These code lists are included in the appendix.

Covariates:

- 1) Age at date of A&G request (categorised)
- 2) Sex
- 3) Geographical region
- 4) CCG pseudonym
- 5) Ethnicity group
- 6) Deprivation (based on IMD quintiles)

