5.2.7 Definition of the study population

All individuals in the CPRD Aurum database, regardless of age, with a first recorded index tracer condition between 01/01/2015 to 31/12/2022 and 24 months prior registration in CPRD Aurum. We will compare outcomes for patients with a recent history of A&G to those with direct referral, stratified by tracer condition. A&G and direct referrals will be obtained from primary care records in the 24 months prior to index (first diagnosis) date. Patients with both A&G and direct referral will be classified based on whichever happened first. We will include age at index date, gender, neighbourhood deprivation, geographical region, and ethnicity, as common covariates for all analyses as well as covariates (e.g. multiple long term conditions) specific to each tracer condition. There is no comparison or control group.

The tracer conditions will be informed from the work in WP1, including interviews with PCCs, and the experiences and advice of our PPIE and Stakeholder groups.

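### WP2 lets the first A&G or routine referral of any specialty in the 24 months before diagnosis set both the exposure group and the start date, so unrelated earlier events can displace the relevant one

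*Protocol*

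**What the plan says.** For WP2a, section 5.3 defines the outcome as "time to diagnosis from the first recorded A&G or direct referral to index diagnosis date". Exposure "will be the initial method of referral (A&G, direct referral) prior to index date". Section 5.2.7 sets the window, "A&G and direct referrals will be obtained from primary care records in the 24 months prior to index (first diagnosis) date", and the rule for patients with more than one type of event: "Patients with both A&G and direct referral will be classified based on whichever happened first". For WP2b, section 5.3 forms four groups from records in the same window, the last being "iv) no recorded A&G or direct referral in the 24 months before diagnosis".

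Section 5.2.8 defines A&G and direct referral only by pointing back to 4.2.8. There, a direct referral is any routine referral to a specialty. Specialty is to be derived for A&G: "We will map A&G to specialty (e.g. rheumatology, neurology) and type of health condition (e.g. musculoskeletal, cardiovascular". That mapping serves the WP1a description by specialty. No sentence in section 5 uses it to decide which events count for a given tracer condition. Section 5.3.3 treats misclassification as random and not seriously biasing.

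For WP1a aim 4, section 4.2.8 begins "To ascertain A&G events which result in a direct referral, we will determine" and then counts referrals within 122 days, with no match on specialty.

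**The concern.** A patient may have several A&G requests or referrals in two years, for different problems. Taking the earliest one favours events that have nothing to do with the tracer condition. Suppose someone has a skin A&G 20 months before a multiple sclerosis diagnosis and a neurology referral 3 months before it. Under the written rule this person is analysed as A&G with 20 months to diagnosis. The pathway that led to the diagnosis was a direct referral taking 3 months. Exposure and outcome are both wrong for that patient, and the same unrelated event causes both errors.

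In WP2b, an unrelated A&G moves a patient from direct referral only to the group with both, or from neither to A&G only.

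Two things are at stake. Unrelated events in the A&G group dilute a true difference. If the two groups contain different shares of unrelated events, their start dates also differ systematically and can produce a difference where none exists. Patients with multiple long-term conditions plausibly have more unrelated referrals. The error may therefore track a factor that the SWAP examines as predictor and moderator, which sits badly with the assumption of random misclassification.

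**Working it through.** **1. The plan's own power (5.2.5).** Inputs: about 11,000 diagnoses (7,000 × 20% × 8 = 11,200, rounded down), 5% exposed to A&G, HR 1.15, 5% significance (two-sided assumed). Everyone in the cohort is diagnosed, so events = 11,000.
- SE of log HR = 1/√(11,000 × 0.05 × 0.95) = 0.0437.
- Power = Φ(ln 1.15/0.0437 − 1.96) = 89.2%, or 89.7% with 11,200. The stated 90% is reproduced.

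**2. Background A&G rate (4.2.5).** The protocol gives "prevalence of A&G of approximately 800/100,000" a year, all specialties. Unrounded: 975,000/9/14 million = 0.774%.

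**3. Share of the assumed 5% that could be background over 24 months.**
- Central: 1 − (1 − 0.00774)² = 1.54%; 1.54/5 = 31%.
- Low, if the same people recur in both years: 0.8/5 = 16%.
- High, if every request is a separate person: 1.7 million/9/14 million = 1.35% a year, 2.70% over two years; 2.70/5 = 54%.

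**4. Dilution if those events carry no signal.** Diluted log HR = (1 − share) × ln 1.15; power as in step 1 with 5% exposed.

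| Background share | Diluted HR | Power |
|---|---|---|
| none | 1.15 | 89% |
| 16% | 1.12 | 77% |
| 31% | 1.10 | 60% |
| 54% | 1.07 | 31% |

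**5. Bias when the groups differ.** The direct-referral rate is not given, so this can only be shown under assumptions. A simulation took no true difference, background start dates uniform over 24 months, truncated-exponential times for relevant events, and 31% background in the A&G group. With 10% background in the direct group, the HR was about 0.74 when the relevant median was 3 months and about 0.86 when it was 6 months. With 40% background in the direct group it was about 1.10 and 1.06. With equal shares it was about 1.0. The direction depends on which group holds more unrelated events.

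**6. Counting only relevant A&G.** If exposure falls from 5% to 5 − 1.54 = 3.46%, power at HR 1.15 with 11,000 events is 76%, and the HR detectable with 90% power is about 1.18.

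**The case against.** The protocol never says that specialty is to be ignored. Section 5 is described as iterative, its data permission is still to be sought, and the tracer conditions are not chosen, so a list of specialties per condition could not be written yet. This stands as a reason why the list itself is absent. It does not remove the point. What section 5 leaves open by name is the tracer conditions and the WP2b outcomes. The rule for exposure and time zero is stated positively, and applied as written it selects the earliest event of any specialty.

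The objection to the size is stronger and largely stands. The 5% comes from a feasibility study in another condition (SLE), and its window and specialty scope are not given. If it was already specialty-specific, dividing 1.54% by it has no meaning. The 0.8% covers A&G of all kinds, and treating all of it as unrelated care is an assumption. It also counts each person once over nine years, which understates annual prevalence for repeat users. An A&G that follows a direct referral does not change the WP2a group.

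A narrow restriction would have its own faults. Section 4.2.8 concedes that A&G records may lack a specialty, so dropping unknowns would probably remove more A&G than direct referrals. A first contact sent to another specialty can also be part of the diagnostic delay.

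A reader might infer that WP1a aim 4 needs same-specialty referral as its main measure. The documents do not support that: the surgical audit cited in section 1.1.2 lists referral to a different specialty (8%) among A&G outcomes.

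**Conclusion.** The point holds as a defect in the WP2 event-selection rule. As written, unrelated earlier events can set both group and start date, and the planned mapping that could prevent this is not applied. This is true whatever the exact share.

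A reader might go further and conclude that a third of the A&G group is background and that the study has 60% power. The documents do not support that. The 31%, HR 1.10 and 60% are an illustration, with ranges of 16% to 54%, 1.12 to 1.07 and 77% to 31%. They require that tracer patients have the general-population A&G rate for unrelated problems, that the 5% covers any A&G in 24 months, and that background events carry no signal. The stated 90% is also not miscalculated on its own inputs. Pure dilution is not assured either, because unrelated direct referrals of unknown frequency could push the estimate either way. WP2 is labelled exploratory, which limits what will be claimed from it but does not make the time to diagnosis measure the intended pathway.

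**What to change.** In 5.2.7 and 5.3, state that exposure and time zero are set only by A&G and direct referrals that meet one of two conditions: a recorded or mapped specialty on a list for that tracer condition, or a relevant symptom code on the day or in the prior 2 weeks. Fix the list when the condition is chosen, and make it broad enough to include plausible first-contact specialties. Apply the same code-based rule to A&G and direct referrals. Report the share of unknown specialty in each group. Run two sensitivity analyses: unknown-specialty events included, and any specialty (the present rule). In 5.2.5, say which window and specialty scope the 5% refers to, and restate the power for the definition adopted.

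For WP1a aim 4, keep any-specialty referral within 122 days as the main measure, describe it as a referral that *followed* the A&G rather than one that *resulted* from it, and report same-specialty referral alongside.

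The work reuses the 4.2.8 mapping, and the WP2 data application is still to come. The cost is that some events are lost or misassigned, probably more among A&G. The exposed group also shrinks, so precision may fall (to about 76% power at HR 1.15 under the central illustration).

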5.2.4 Outcomes to be measured

For WP2a, the outcome for those with an A&G and/or direct referral recorded will be the time to diagnosis from the first recorded A&G or direct referral to index diagnosis date.

For WP2b, outcomes will be guided by our PPIE and Stakeholder groups as well as emerging results from interviews with PCC's. They are likely to include in the 12 months following referral:

- i. Number of consultations recorded in primary care;
- ii. Number of prescriptions recorded in primary care;
- iii. Number of referrals recorded in primary care;
- iv. AE attendance recorded in HES AE
- v. Number of additional outpatient appointment recorded in HES outpatients
- vi. Overnight unplanned hospital admission recorded in HES APC (admitted patient care);
- vii. Mortality recorded in ONS.

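### Protocol sections 5.2.4, 5.2.7 and 5.3 do not give WP2b one workable time zero: outcomes run from referral, but the four comparison groups are settled only at diagnosis

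*Protocol*

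**What the plan says.** Three sections of the Protocol bear on the WP2b comparison.

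- **Clock (5.2.4).** The WP2b outcomes are introduced with "They are likely to include in the 12 months following referral". The list includes "Number of referrals recorded in primary care", alongside consultations, prescriptions, A&E attendance, outpatient appointments, unplanned admission and mortality.
- **Groups (5.3).** For WP2b, "individuals with each index condition will be categorised as i) A&G only, ii) direct referral only, iii) A&G and direct referral", and the last group is "iv) no recorded A&G or direct referral in the 24 months before diagnosis". Negative binomial or zero-inflated models are then to "estimate incidence rate ratios for the number of consultations, referrals and prescriptions in primary care, and number of outpatient appointments". Robust Poisson models serve A&E and unplanned admission, and flexible parametric survival models serve mortality.
- **Ascertainment and classification (5.2.7).** "A&G and direct referrals will be obtained from primary care records in the 24 months prior to index (first diagnosis) date". The same section adds: "Patients with both A&G and direct referral will be classified based on whichever happened first". That section covers WP2a and WP2b and does not limit the rule to either.

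For WP2a, section 5.3 takes the initial method of referral as the exposure.

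**The concern.** A comparison counted forward from a start date needs groups that are known on that date. Here the start is the referral, but the label A&G only, direct only or both can be assigned only once the whole interval up to diagnosis has been seen. Three things follow if the text is run as it stands.

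1. **Sorting on later events.** A patient diagnosed soon after the first event has little time to acquire a second one, so quick diagnoses collect in the only groups and slow ones in the both group. Any outcome related to time to diagnosis then differs between groups without a pathway effect. Covariate adjustment does not remove this.
2. **Partial circularity for referrals.** An A&G-only patient has no direct referral between the A&G and diagnosis, by definition. A both-group patient whose A&G came first, with the referral inside the 12 months, has at least one. The model then estimates a rate ratio for referrals between these groups.
3. **Undefined start dates.** The neither group has no referral to count from. The both group has two events, and the text does not say which one starts the clock.

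At stake is whether WP2b's ratios say anything about A&G against direct referral, or partly report how patients were sorted.

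**Working it through.** **The plan's own figure.** The only WP2 calculation (5.2.5) is 90% power for a hazard ratio of 1.15 with about 11,000 diagnoses and 5% receiving A&G. It concerns time to diagnosis (WP2a).
- Events needed (Schoenfeld, two-sided 5%): (1.960 + 1.282)² / [0.05 × 0.95 × (ln 1.15)²] = 11,325.
- Power with 11,000 events: √(11,000 × 0.0475) × ln 1.15 − 1.960 = 1.235, i.e. 89.2%.

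The figure reproduces, so sample size is not the issue.

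**When each item is known, reading 5.2.4 and 5.3 literally**

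| Group | Start of the 12 months | When membership is known |
|---|---|---|
| i A&G only | the A&G (no direct referral exists) | diagnosis |
| ii direct only | the direct referral | diagnosis |
| iii both | A&G or direct referral, not stated | at the second event |
| iv neither | none exists | diagnosis |

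**Null simulation of the referral count.** The first-event type affects nothing later, so the true rate ratio is 1.00.
- From the Protocol: 50% of A&Gs followed by a referral (planning value, 4.2.5); the 122-day window (4.2.8); the 24-month look-back (5.2.7); the 12-month outcome window (5.2.4).
- Assumed: the 50% applies to the 122 days and also to further direct referrals after a direct referral; 5% chance of a further A&G in 122 days; 50:50 split of first events; Poisson referrals; exponential time to diagnosis with median 60, 180 or 365 days; the first event itself is not counted.

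| Median days to diagnosis | i v ii | iii v ii | A&G-first v direct-first |
|---|---|---|---|
| 60 | 0.84 | 1.29 | 1.00 |
| 180 | 0.72 | 1.18 | 1.00 |
| 365 | 0.67 | 1.15 | 1.00 |

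With 25% or 10% in place of 50%, i v ii spans 0.43-0.81 and iii v ii spans 1.51-2.94. The first-event rule stays at 0.997-1.009.

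**Closed-form check, 180-day median**
- Referral rate r = ln 2/122 = 0.00568 per day; diagnosis rate d = ln 2/180 = 0.00385; s = r + d = 0.00953.
- Direct only: 365r = 2.07 referrals.
- A&G only: given no earlier referral, time to diagnosis is exponential with rate s, cut at 730 days. Mean referrals = r × [365 − (1 − e^(−365s))/s] / (1 − e^(−730s)) = 0.00568 × (365 − 101.7)/0.999 = 1.50. Ratio 1.50/2.07 = 0.72.
- Share of A&G-first patients ending as A&G only: (d/s)(1 − e^(−730s))/(1 − e^(−730d)) = 0.429. A&G-first patients average 2.074 overall, so those in the both group average (2.074 − 0.429 × 1.498)/0.571 = 2.51.
- About 8.3% of direct-first patients also reach the both group, averaging 2.07. At a 50:50 split: (0.571 × 2.507 + 0.083 × 2.074)/0.654 = 2.45. Ratio 1.18.

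This agrees with the simulation.

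**Sensitivity to the split.** The i v ii ratio does not depend on it; iii v ii does. With 5% of patients A&G-first (an assumption borrowing the 5% of 5.2.5): (0.05 × 0.571 × 2.507 + 0.95 × 0.083 × 2.074)/(0.0286 + 0.0789) = 2.19, a ratio of 1.06 instead of 1.18.

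**The case against.** **The clock is provisional.** The outcome list is worded as likely, WP2 is to be designed iteratively, and data permission is still to be sought. The groups in 5.3 are defined by the 24 months before diagnosis, which fits follow-up from diagnosis. With that clock, all four groups are baseline groups and every problem above disappears. This stands as a reason to frame the point as a missing common time zero. It does not remove the point, because 5.2.4 names referral as the start and no section names diagnosis.

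**5.3 need not contradict 5.2.7.** A reader might infer a flat contradiction with the first-event rule. Section 5.3 uses initial method for WP2a, and section 1.3 sets out the same four types for describing patients, so the rule may be meant for WP2a's two-level exposure. The documents do not settle this, because 5.2.7 carries no such limit. A clarifying phrase is needed, and the time-zero problem remains under either reading.

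**WP2b is descriptive.** Describing use of care by completed pathway is legitimate, provided it is counted from diagnosis. But WP2b also plans adjusted rate and hazard ratios, and objective 2b compares the two pathways. The confounding plan (5.3.1) mentions only unmeasured factors such as severity.

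**Circularity is narrow.** This stands. The listed referral count is not restricted to routine direct referrals, whereas the exposure definition in 4.2.8 excludes fast-track and emergency ones. An A&G-only patient is certain of zero direct referrals over the full 12 months only if diagnosis comes at least 12 months after the A&G: 0.2% to 27% of that group across all the simulated scenarios. Where the direct referral came first in the both group, no further referral is guaranteed.

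**Conclusion.** The concern holds in this form: 5.2.4, 5.2.7 and 5.3 do not supply one start date at which every WP2b group exists and is known. Run literally, one group cannot be placed on the clock, one has an ambiguous start, and the remaining contrasts are biased by sorting on later events.

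For the direct-referral count at the 50% planning value, the distortion under no true effect is about 0.67-0.84 (A&G only v direct only) and 1.15-1.29 (both v direct only), against 1.00 for the first-event rule. The direction follows from the definitions. The size rests on the assumed hazards, the times to diagnosis and, for the both group, the split of first events.

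Two stronger readings are not supported. A reader might infer that WP2b's ratios generally are fixed by definition. That applies only to direct referrals, and only between the first event and diagnosis; for the other utilisation outcomes the fault is bias, whose size the documents do not allow one to state. A reader might also point to the gap in time to diagnosis that the sorting creates. With equal, independent, assumed hazards and a 9-month median it is 4.3 months in A&G only against 11.8 in both. That shows the mechanism, but WP2b plans no comparison of time to diagnosis across the four groups.

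**What to change.** Reconcile the three sections by stating one time zero per analysis and fixing exposure at it.

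- **Outcomes counted from referral:** compare A&G-first with direct-referral-first, as in 5.2.7, starting at the first event. Leave out the neither group. Report later conversion from A&G to direct referral as an outcome.
- **Four groups:** use them for describing patients, or for outcomes counted from diagnosis, when all four are known at the start.
- **Mortality:** start at diagnosis. Entry to the cohort requires a diagnosis (5.2.7), so a clock starting at referral would build guaranteed survival time into the model.
- **5.2.7:** say whether the first-event rule covers WP2b.

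The cost is protocol wording before the WP2 data application, with the same data and model families. The downside is that the four-group contrasts would no longer cover the period before diagnosis.

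### Counting WP2b mortality from referral in a cohort selected on later diagnosis makes the referral-to-diagnosis interval immortal, and biases the comparison towards whichever pathway diagnoses more slowly

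*Protocol*

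**What the plan says.** Three parts of the Protocol bear on the WP2b mortality comparison.

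- **Cohort (5.2.7).** Patients enter "with a first recorded index tracer condition between 01/01/2015 to 31/12/2022 and 24 months prior registration in CPRD Aurum". Exposure lies before entry: "A&G and direct referrals will be obtained from primary care records in the 24 months prior to index (first diagnosis) date".
- **Window (5.2.4).** Of the WP2b outcomes it says: "They are likely to include in the 12 months following referral". Item vii on the list is "Mortality recorded in ONS".
- **Model (5.3).** Patients are put into four groups, the last being "iv) no recorded A&G or direct referral in the 24 months before diagnosis". For deaths, "flexible parametric survival analysis will estimate hazard ratios for mortality". The section gives no time origin, delayed entry or landmark for this model.

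The plan also intends to look for a difference in delay between the pathways. For WP2a, "We will use flexible parametric survival analysis to compare A&G and direct referral on time to diagnosis". The sections on confounding (5.3.1) and limitations (5.3.3) cover unmeasured confounding, misclassification and incomplete coding. They do not mention survival to diagnosis as a condition of entry.

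**The concern.** A referred patient who dies before the tracer diagnosis never enters the cohort. Every cohort member has therefore survived the interval from referral to diagnosis by construction. If the mortality clock starts at referral and that interval counts as time at risk, it adds person-time but can add no deaths. A patient diagnosed more than 12 months after referral cannot have the outcome in the window at all.

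The amount of immortal time is the time to diagnosis, which is the quantity WP2a compares. Any pathway difference there carries over into the mortality hazard ratio and flatters the slower pathway. Covariate adjustment does not remove it, because the cause is the definition of risk time and not patient mix. At stake is the one outcome on the list that speaks most directly to whether A&G is safe.

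**Working it through.** **The plan's own figures.** The Protocol gives no figure for mortality. Its one WP2 power statement (5.2.5) concerns time to diagnosis. With 5% on A&G, a hazard ratio of 1.15, 90% power and 5% two-sided, the Schoenfeld formula gives (1.960 + 1.282)² / (0.05 × 0.95 × (ln 1.15)²) = 11,325 events, against the stated 11,000 or so. That reproduces, but it does not bear on this point.

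**Inputs.** The window of 12 months from referral is from 5.2.4, and the maximum of 24 months from referral to diagnosis is from 5.2.7. Delay distributions and mortality rates are not in the document. I assume exponential delays T truncated at 24 months, constant mortality equal in both pathways, and hence a true ratio of 1.

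**Step 1: share of the window in which a death can be observed.** At low mortality this share is E[max(12 − T, 0)] / 12. For nominal mean m it equals

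(12 − m(1 − e^(−12/m))) / (12 × (1 − e^(−24/m))).

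- m = 3: 9.055 / (12 × 0.9997) = 0.755
- m = 4: 8.199 / (12 × 0.9975) = 0.685
- m = 6: 6.812 / (12 × 0.9817) = 0.578
- m = 8: 5.785 / (12 × 0.9502) = 0.507
- m = 9: 5.372 / (12 × 0.9305) = 0.481

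**Step 2: apparent mortality rate ratio, slower v faster pathway.**

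- 3 v 4 months: 0.685 / 0.755 = 0.91
- 3 v 6 months: 0.578 / 0.755 = 0.77
- 4 v 8 months: 0.507 / 0.685 = 0.74
- 6 v 9 months: 0.481 / 0.578 = 0.83

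These means are nominal. After truncation, 4 v 8 becomes 3.9 v 6.7. If delays were instead capped at 24 months (longer ones set to 24), the ratios would be 0.75 (3 v 6), 0.71 (4 v 8) and 0.79 (6 v 9).

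**Step 3: simulation.** Patients were kept only if alive at diagnosis. Deaths and person-time were counted for 12 months from referral, with mortality of 2, 10 or 30 per 100 person-years. The ranges below run over the three rates.

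| Nominal means (months) | Apparent ratio, clock from referral |
|---|---|
| 3 v 3 | 0.99–1.00 |
| 3 v 4 | 0.90–0.92 |
| 3 v 6 | 0.76–0.79 |
| 3 v 9 | 0.64–0.67 |
| 6 v 9 | 0.83–0.85 |
| 6 v 12 | 0.74–0.76 |

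At 10 per 100 person-years and 3 v 6 months, immortal time is 25% v 42% of counted person-time. The apparent 12-month risks are 7.3% v 5.7%, where unconditional follow-up would give 1 − e^(−0.10) = 9.5% in both. Absolute risks are thus too low even where the ratio is unbiased.

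**Step 4: the remedy.** With risk time starting at diagnosis, either as time zero or as delayed entry on the referral clock, the ratio returns to 0.99–1.01 in every scenario.

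**Step 5: the four groups.** Group iv has no referral in the look-back period, so there is no date from which to count its 12 months. The stated window cannot be applied to the full comparison in 5.3.

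**The case against.** The strongest reply is that the Protocol does not fix a referral-origin model. Section 5.3 names no origin, the outcome list in 5.2.4 is provisional, and the opening of section 5 says WP2 will be designed iteratively. An analysis plan could specify delayed entry. The index date is defined as diagnosis, and group iv already forces some other origin. WP2 is also labelled descriptive and exploratory.

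Much of this stands. A reader might infer that the model is certain to count the interval as time at risk; the text does not go that far. But the referral window is the only one stated, mortality is listed under it, and the diagnosis-conditioned cohort is not worded as provisional. The two conflict as written, so this is not merely a detail left for later. The exploratory label does not help either, because adjusted hazard ratios for mortality are planned.

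Two further inferences would also be too strong. One is that A&G will look safer: the Protocol does not say which pathway is slower, and with equal delays the A&G v direct ratio is unbiased. The other is that a harmful delay would appear as a survival benefit. The bias masks harm but need not reverse it. At 3 v 6 months, a true ratio after diagnosis of about 1 / 0.77 = 1.30 would look like no difference, and a larger one would still show as harm.

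**Conclusion.** The concern holds in a conditional form. Followed as written, 5.2.4, 5.2.7 and 5.3 make referral-to-diagnosis time immortal. If the pathways differ in time to diagnosis, the mortality hazard ratio is biased in favour of the slower one and could mask harm from delay. The size depends on delays that the Protocol does not give: under the assumptions above it is about 0.91 for a one-month gap (3 v 4), 0.77 for 3 v 6 and 0.74 for 4 v 8, against a true ratio of 1. These are illustrative rate ratios, not predictions of the fitted hazard ratio. Separately, and with no assumption, the referral window cannot apply to group iv.

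**What to change.** In 5.2.4 and 5.3, start mortality risk time at the diagnosis (index) date for all four groups. For comparisons among the referred groups only, a referral origin with delayed entry at diagnosis can be added as a sensitivity analysis; it cannot cover group iv.

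State two limits alongside the results. Deaths before diagnosis cannot be seen in this cohort; only a cohort defined at referral, whatever the later diagnosis, could show them. A diagnosis origin is also open to lead time when one pathway diagnoses earlier.

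Splitting the utilisation counts into time before and after diagnosis is optional. Total use in the 12 months after referral is a legitimate descriptive quantity for objective 2b, though group iv needs its own origin there too.

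The cost is wording and one change to the survival set-up. If the 12-month length is kept, the latest deaths needed fall at the end of 2023, essentially as under a referral window, so no extra data are required. WP2 data permissions are still to be sought, so the change can be made before the application. The price is in interpretation: the mortality results will describe survival after diagnosis only, and not the safety of the whole path from referral.
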